1.1 Primary Objective

Primary Objective: *To evaluate the safety of multiple ascending intravenous (IV) doses of 3K3A-APC following recombinant tissue plasminogen activator (tPA) administration, mechanical thrombectomy, or both in subjects who have experienced moderate to severe acute ischemic stroke.*

It is hypothesized that, using the continual reassessment method, at least one of the proposed 3K3A-APC doses will be safe enough to carry forward to future clinical studies.

1.2 Secondary Objectives

Secondary Objective 1: *To investigate the pharmacokinetic (PK) properties of 3K3A-APC following tPA, mechanical thrombectomy, or both in adults with acute ischemic stroke.*

Secondary Objective 2: *To evaluate the effect of 3K3A-APC on the presence of tPA / mechanical thrombectomy-related bleeding (hemorrhage and microbleeds) in the brain as determined by MRI at Day 30.*

It is hypothesized, based on preclinical studies, that 3K3A-APC will reduce the expected recanalization therapy-related bleed rate.

2. PRIMARY ENDPOINT

The primary objective of the study is to evaluate the safety of multiple ascending intravenous (IV) doses of 3K3A-APC following tPA administration in subjects who have experienced moderate to severe acute hemispheric ischemic stroke. Safety will be assessed by defining dose limiting toxicities (DLTs), which will be graded using the National Cancer Institute (NCI) Common Terminology Criteria for Adverse Events (CTCAE), Version 4.03.

DLTs will be assessed from the first dose to 48 hours following the last dose of study treatment (unless specified below), and defined as any of the following AEs that have an attribution of “related” to study treatment (possibly, probably and definitely):

- An activated partial thromboplastin time (aPTT) that reaches 2x the upper limit of normal (ULN) at 1 hour post-dose. The ULN range is defined locally by the site laboratory.
- Symptomatic intracranial hemorrhage (SICH) defined as blood present on CT or MRI brain image that is associated with clinical worsening that meets the definition of neuroworsening (4 or more point increase on the NIHSS; see section 10.3 for definition) *and* in the opinion of the investigator represents a clinically significant change that can be attributed to the hemorrhage. Subarachnoid hemorrhage that occurs in subjects who receive mechanical thrombectomy will NOT be considered a DLT, and instead will be evaluated in an exploratory analysis upon study completion.
- Findings that meet all of the following three components (Hy’s Law):
 - $\geq 3x$ ULN of alanine aminotransferase (ALT) or aspartate aminotransferase (AST)
 - Serum total bilirubin (TBL) $> 2x$ ULN, without initial findings of cholestasis [serum alkaline phosphatase (ALP) activity $> 2x$ ULN]
 - And, no other reason can be found to explain the combination of increased aminotransferase (AT) enzymes and TBL, such as viral hepatitis A, B, or C, pre-existing or acute liver disease, or another drug capable of causing the observed injury.
- Any other bleeding event classified as serious by the Investigator, or any bleeding that required the administration of more than 2 units of packed red cells over any two consecutive days.
- Any Grade 3 laboratory value that, in the opinion of the investigator, is related to study treatment.

- Any adverse event that, in the opinion of the investigator, is related to study treatment and leads to cessation of further dosing.

The SRC will review the safety data for each potential DLT, and make a final determination as to whether or not an incident should be classified as a DLT. Reported DLTs that are considered possibly related to study drug but definitely related to another event will not be considered DLTs upon final adjudication. An example of such an event would be an elevated aPTT following the first dose in a subject who undergoes mechanical thrombectomy during which heparin is administered; the elevated aPTT can be attributed to the heparin and therefore should NOT be considered a DLT in this isolated instance. Another example would be the occurrence of hypofibrinogenemia in a subject who receives tPA. Low fibrinogen levels can be attributed to the tPA, and there is a documented rate of occurrence of 11% in subjects receiving tPA (Genentech, 2015). Furthermore, 3K3A-APC does not cause a reduction in the level of fibrinogen in plasma and therefore this finding should NOT be considered a DLT.

3. SECONDARY ENDPOINTS

3.1 Pharmacokinetic (PK) Properties

One secondary objective of this study is to investigate the PK properties of 3K3A-APC following tPA administration in stroke subjects. PK blood samples will be collected from approximately 40 subjects at a subset of study sites to ensure adequate sampling across all dose levels. Samples should be collected following one of the doses of 3K3A-APC at the following time points: end of infusion and 20, 40, 60, and 80 minutes after the end of infusion (5 total samples per subject). The investigator can decide which dose (dose 2-5) will be used for PK collection. Collection of samples outside of the requested nominal time will not be a protocol deviation, but it is essential that the actual time of collection be captured for analysis. Samples collected for PK will only be used for PK-related analysis and method development.

PK parameters following administration of 3K3A-APC in the study will be determined using concentration data obtained via the enzyme-immunocapture assay of 3K3A-APC amidolytic activity in plasma. PK parameters will be determined by fitting a compartmental model to each subject's data. Individual subject observed and model-predicted plasma concentration over time by treatment group will be plotted on linear and semi-logarithmic axes. Descriptive statistics of PK parameters will be provided for each dose level. Additionally, the pharmacokinetic-pharmacodynamic relationship between the change from baseline in aPTT and the concurrently measured 3K3A-APC plasma concentration will be evaluated 1 hour after the end of infusion.

3.2 Hemorrhage Rates

Another secondary objective of the study is to evaluate the effect of 3K3A-APC on the incidence of tPA / mechanical thrombectomy-related bleeding in the brain. Imaging will be used to assess the development of recanalization therapy-related hemorrhage seen on susceptibility-weighted magnetic resonance imaging (MRI). Each subject is expected to have two standard of care (SOC) imaging scans:

- Baseline Scan: Non-contrast CT or MRI (with prior approval), per local SOC
- 24-36 Hour Scan: Non-contrast enhanced head CT or MRI, per local SOC, 24-36 hours following tPA bolus administration if subject receives any IV tPA or 24-36 hours following mechanical thrombectomy if subject does not receive any IV tPA

These scans should be performed according to local SOC. Each site should use its standard stroke imaging protocol for CT scans. If MRI is performed as SOC at either time point, it is preferred that the MRI protocol for the study be used. We expect 80% of these 24-36 hour scans to be CT scans, and 20% to be MRI.

Additionally, each subject will have three trial-mandated scans:

- Day 7 / Discharge Scan: MRI: T1 and T2 weighted images, as well as DWI and susceptibility weighted imaging (SWI) sequences must be performed for all subjects on Day 7 or just prior to discharge, whichever occurs first. If the subject is discharged before Day 4, then it is expected that he/she return for Day 7 assessments or arrangements be made to collect this information from the treatment facility where the subject was transferred if the subject is unable to return.
- Day 30 Scan (+/- 5 Days): MRI: T1 and T2 weighted images, as well as DWI and SWI sequences must be performed for all subjects.

- Day 90 Scan (+/- 10 Days): MRI: T1 and T2 weighted images, as well as DWI and SWI sequences must be performed for all subjects. While MRI is preferred at Day 90, should a subject become unable to undergo MRI, a CT scan is allowed instead.

These trial-mandated scans should be performed on a 1.5T machine, with slice thickness between 2.5 and 7.5 mm, and will be used to evaluate secondary and exploratory outcomes in this study. The effect of 3K3A-APC on the presence of tPA/mechanical thrombectomy-related hemorrhage in the brain will be determined by 1.5T MRI at Day 30. Day 30 MRI scans will be collected and evaluated by a central radiologist for the presence of hemorrhage and by computerized assessment for microbleeds. Since patients will not necessarily have a baseline MRI, post-recanalization microbleeds (defined as SWI hypointensities less than 5mm in diameter) will be counted as tPA/mechanical thrombectomy-related only if found within the ischemic territory (Kimura et al, 2013). All other areas of SWI hypointensity larger than 5mm in diameter will be counted as tPA/mechanical thrombectomy-related regardless of the territory in which they are found.

The Central Reader's assessment of the scans will be recorded in the study database. The relevant form collects data on whether the scan is normal or not, presence of past strokes and/or edema, qualitative data for edema, quantitative data regarding hemorrhage location and volume, number and location of microbleeds, and stroke lesion volume. Only the questions that are pertinent to the type of scan (CT or MRI) will be enabled in the database, as some questions do not apply to all types of scans. The objectives of this central review are to:

- Qualitatively assess each subject's scan for:
 - Presence and location of hemorrhage (hematoma or petechiae) on all scans
 - Presence and location of microbleeds on MRI scans
 - Presence and location of edema on all scans
- Quantitatively assess each subject's scan for:
 - Volume of hemorrhage on all scans
 - Number of microbleeds on MRI scans
 - Infarct volume at Baseline and Day 90

Given the different imaging protocols used in this study, bleeding volume quantification will be retrieved from susceptibility sensitive sequences directly. All data will be processed using SPIN Software (Signal Processing in MRI, Magnetic Resonance Innovations, Detroit, MI). In order to accurately quantify bleeding volume, only hypointensities likely to be caused by bleeding will be deemed aberrant. These include: large bleeds, microbleeds, linear bleeding regions, iron deposition along vein paths, and pooled intraventricular blood. The processor will avoid blood vessels, calcifications, artifacts, and areas outside of normal brain parenchyma. In cases where Susceptibility Weighted Imaging (SWI) magnitude and phase are collected, Quantitative Susceptibility Mapping (QSM) will be used to confirm calcifications. However, given the nature of gradient echo imaging, some calcifications may be misrepresented when not accompanied by phase data. This will be mitigated by careful consideration of location and morphology on sequences available. Areas avoided due to the likelihood of calcifications will be: the falx, choroid plexus, pineal gland, globus pallidus, and parenchymal edges near bony structures (sinuses, ears). For instance, a small hypointensity located in the choroid plexus will not be considered aberrant. Some exceptions may be made based on accompanying sequences, especially when QSM or phase was available. A large bleed extending into the falx will be considered aberrant. A small hypointensity in the globus pallidus that is hyperintense on QSM will be considered aberrant.

For processing, two objects will be drawn for each scan. One will include all aberrant hypointensities outside of the infarct. Another will include all aberrant hypointensities within or reaching the infarct. A region of interest (ROI) containing normal appearing white matter will then be selected. The average intensity within this ROI will be obtained and halved. This value will be the threshold used for the bleeding volume quantification. The number of pixels lower than the threshold will be produced through SPIN software. The volumes of each thresholded object within the sequence will be calculated using the Cavalieri method with slice thickness including any gaps in data collection. To estimate the incidence of hemorrhage at Day 30, we define hemorrhage as hematoma + petechial bleeding and exclude microbleeds. Therefore, a Day 30 image will be considered "positive for hemorrhage" if the corresponding total hematoma volume by planimetry is larger than 0.06 mL (5 mm). However, this cutoff value is imperfect because a patient with two microbleeds totaling more than 0.06 mL should not be considered hemorrhage positive since each lesion would be <5 mm. In order to account for the uncertainty in the optimal definition of "hemorrhage positive", several alternative cut points will be implemented for sensitivity analysis:

- PRIMARY - Positive if total hematoma volume by planimetry (Question 7 on the Imaging Review Form) > 0.06mL (5 mm diameter)
- SENSITIVITY
 - Positive if total hematoma volume by planimetry > 0
 - Positive if total hematoma volume by planimetry > 0.5 mL (10 mm)
 - Positive if total hematoma volume by planimetry > 1.8 mL (15 mm)

The number of cerebral microbleeds (Question 8 on the Imaging Review Form) will be identified using the following parameters:

- Round or ovoid (rather than linear)
- Black on T2*-Weighted MRI
- Blooming on T2*-Weighted MRI
- Dipole effect in SWI phase
- Bright on SWIM
- Hypointense or not visualized on T1 and FLAIR
- Isolated (can be verified as isolated and not a vessel using SWI mIP)
- Devoid of signal hyperintensity on T1- or T2-Weighted sequences
- At least half surrounded by brain parenchyma
- Distinct from other potential mimics, such as iron/calcium deposit, bone, or vessel flow

A scan will be considered positive for microbleeds if a nonzero value is entered into the within stroke territory section (Question 8a on the Imaging Review Form).

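### The primary Day 30 hemorrhage rule tests a summed volume that can include microbleeds, so microbleed-only scans can be classed as positive, and no sensitivity row enforces the exclusion

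*SAP*

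**What the plan says.** All of this is in SAP section 3.2 unless stated otherwise.

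- **Definition.** For Day 30 incidence, "we define hemorrhage as hematoma + petechial bleeding and exclude microbleeds". Microbleeds are "defined as SWI hypointensities less than 5mm in diameter".
- **What is measured.** Hypointensities likely to be bleeding are quantified. "These include: large bleeds, microbleeds, linear bleeding regions, iron deposition along vein paths, and pooled intraventricular blood". Two pooled objects are drawn per scan: "One will include all aberrant hypointensities outside of the infarct", and "Another will include all aberrant hypointensities within or reaching the infarct". Volumes come from the Cavalieri method, on scans "with slice thickness between 2.5 and 7.5 mm".
- **Primary rule.** "Positive if total hematoma volume by planimetry (Question 7 on the Imaging Review Form) > 0.06mL (5 mm diameter"). It contains no test of individual lesion size.
- **Admission.** "this cutoff value is imperfect because a patient with two microbleeds totaling more than 0.06 mL should not be considered hemorrhage positive", the reason given being that each lesion is under 5 mm.
- **Sensitivity rows.** The same total is cut at > 0, > 0.5 and > 1.8 mL.
- **Reporting.** SAP section 8.2, Table 3 shows these four volume rows and a separate microbleed row. The microbleed row uses the within-territory count (Question 8a). Treated and placebo subjects are compared by Pearson chi-square, or by Fisher's exact test where expected counts are small.

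**The concern.** The definition works lesion by lesion, while the rule works on a total. A total cannot tell one 5 mm hematoma from several smaller microbleeds, so the rule can give an answer that the definition forbids. The stated remedy moves the cut-off on the same total and never applies the exclusion.

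The comparison at stake is a key secondary one, tested at 0.05 (SAP section 6). If microbleeds drive some positives, the hemorrhage rows and the microbleed row share lesions and cannot be read as separate findings. If the total covers both objects, microbleeds outside the infarct also contribute, although section 3.2 treats microbleeds as therapy-related only within the ischemic territory. Because the volume is area times slice thickness, a small lesion's classification can also depend on the scanner setting.

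**Working it through.** **1. The SAP's cut-offs.** Sphere volume is πd³/6, with 1 mL = 1000 mm³. Diameters of 5, 10 and 15 mm give 0.0654, 0.524 and 1.767 mL, against the stated 0.06, 0.5 and 1.8 mL. The cut-offs are therefore rounded sphere volumes. Inverting, 0.06 mL corresponds to d = 4.86 mm.

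**2. Several microbleeds.** One 4 mm sphere is π × 64/6 = 33.5 mm³ = 0.0335 mL, so two total 0.067 mL, which is positive. Two equal lesions reach the cut-off at (6 × 30/π)^(1/3) = 3.86 mm each, and three at (6 × 20/π)^(1/3) = 3.37 mm each.

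**3. One microbleed on thick slices.** Take a 4 mm sphere (radius 2 mm), sampled at slice centres, with its position relative to the slices uniform. When one slice centre hits it at offset z, the Cavalieri volume is t × π(4 − z²).

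| Slice t | Condition for > 60 mm³ | Share of positions | Maximum (mL) |
|---|---|---|---|
| 2.5 mm | never met | 0% | 0.038 (two slices, z = ±1.25) |
| 5 mm | 4 − z² > 3.820, so \|z\| < 0.425 | 0.849/5 = 17% | 0.063 |
| 7.5 mm | 4 − z² > 2.546, so \|z\| < 1.206 | 2.411/7.5 = 32% | 0.094 |

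**4. The sensitivity rows.**
- At > 0 mL, any measured microbleed makes the scan positive.
- At > 0.5 mL, 0.5/0.0654 = 7.6, so at least 8 microbleeds just under 5 mm are needed.
- At > 1.8 mL, 1.8/0.0654 = 27.5, so at least 28 are needed.
- The two higher cut-offs also exclude single hematomas of about 5-10 and 5-15 mm, which meet the definition.

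**5. Effect on the comparison (illustration only).** Let p₁ and p₂ be the placebo and treated rates, n₁ = 22, n₂ = 66, and p̄ the pooled rate. Power is Φ{[(p₁ − p₂) − 1.96√(p̄(1 − p̄)(1/n₁ + 1/n₂))] / √(p₁(1 − p₁)/n₁ + p₂(1 − p₂)/n₂)}. For 40% v 10%, p̄ = 0.175 and this is Φ[(0.300 − 0.183)/0.111] = 85.4%. Table 6 of SAP section 9.2 gives 85%, and the same formula reproduces all 18 cells of that table within 2 points.

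Now assume that a share m of truly negative scans flips to positive, equally in both arms, so that each rate becomes p + (1 − p)m:

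| m | Placebo v treated | Power |
|---|---|---|
| 0 | 40% v 10% | 85.4% |
| 5% | 43% v 14.5% | 77.5% |
| 10% | 46% v 19% | 69.3% |
| 20% | 52% v 28% | 53.8% |
| 30% | 58% v 37% | 40.7% |

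The equal-flip assumption matters. With m = 10% in both arms the difference shrinks from 30 to 27 points. If m = 10% in placebo and 0 in treated, because the drug suppresses microbleeds, it becomes 46% v 10%, or 36 points, and overstates the effect on hemorrhage. The documents supply no value of m for either arm.

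**The case against.** The SAP discloses the weakness, brackets it with lower and higher cut-offs, and reports microbleeds in their own row. The primary rule names a total hematoma volume (Question 7), and the form itself is not among the documents, so exactly what enters that total is partly inferred. This has some force, but the SAP's caveat about two microbleeds makes sense only if microbleeds can enter the total. Disclosure and moved cut-offs still leave no row that applies the definition.

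Three stronger readings are tempting, and the documents do not support them.

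- **All microbleed-only scans are counted as hemorrhage.** Only those whose summed volume exceeds 0.06 mL can be.
- **One 4 mm microbleed measures 0.063 or 0.094 mL on 5 or 7.5 mm slices.** Those are maxima; most positions give less, or miss the lesion. The SAP's threshold at half of white-matter intensity could lower them further. With simple partial-volume averaging of a signal-void 4 mm sphere and no blooming, the maximum would be 0.038 mL at 5 mm and 0.011 mL at 7.5 mm. Blooming pushes the other way. The slice effect is plausible, but its size is not established.
- **The sensitivity rows do nothing.** The > 0.5 and > 1.8 mL rows largely remove microbleed-only positives, at the price of small hematomas.

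**Conclusion.** The point holds in a limited form: the primary rule can classify microbleed-only scans as hemorrhage positive against the SAP's own definition, and no planned row enforces the exclusion. The two-lesion case rests on the SAP's admission and sphere geometry. The single-lesion case (17% and 32% of positions) rests on ideal slice-centre sampling of a 4 mm sphere and ignores intensity thresholding and blooming.

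A reader might infer that the error must dilute the treatment difference. That needs misclassification unrelated to treatment. SAP section 1.2 hypothesises that the drug reduces recanalization-related bleeding, under an objective that includes microbleeds, and Protocol section 2.4.1 reports microhemorrhages eliminated in animals, so the bias could go either way. The power figures above show sensitivity to an assumed m and do not estimate the loss in this trial. The change should be made because it is cheap and removes an ambiguity in a key secondary result.

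**What to change.** Add to SAP section 3.2, and to Table 3 at least as the first sensitivity row, one pre-specified rule that applies the exclusion. Keep the volume-only rule beside it.

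- **(a)** Positive if Question 7 volume > 0.06 mL and the central reader recorded hematoma or petechiae. Section 3.2 lists that presence call among the central review objectives. First confirm that the central-read problems mentioned in the SAP's Summary of Changes for version 2.0 do not affect this field.
- **(b)** Positive if Question 7 volume > max(1, Question 8 microbleed count) × 0.065 mL, the 5 mm sphere. The count should cover the same region as the volume.

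Do not use slice-specific thresholds in (b). A single-slice figure at 2.5 mm would be π × 25/4 × 2.5 = 49 mm³ = 0.049 mL, below the present cut-off, and slice thickness is not among the recorded items that the SAP lists.

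The cost is SAP wording and a few lines of code, with no re-reading of scans if these fields are held as described. Under (b), a small hematoma in a patient with many microbleeds could be missed. Rule (b) also leaves some slice dependence: on 7.5 mm slices a lone 4 mm lesion still exceeds 0.065 mL when 4 − z² > 65/(7.5π) = 2.759, so |z| < 1.114 mm, or 2.228/7.5 = 30% of positions.

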4. ENROLLMENT & RANDOMIZATION

After beginning tPA or mechanical thrombectomy for moderate to severe acute hemispheric ischemic stroke, subjects or their legally authorized representatives will be presented with the study details and the informed consent form (ICF). All code stroke patients arriving at the site who receive tPA will be considered for this study. In addition, patients ineligible for tPA but considered candidates for mechanical thrombectomy alone, and who can begin intra-arterial therapy within 6 hours of symptom onset, will also be considered for this study. Written informed consent will be obtained from each study participant or his/her legally authorized representative before any study-specific procedures or assessments are performed. Once the consent form has been signed, the subject is considered enrolled in the study. Administration of tPA or initiation of mechanical thrombectomy should not be delayed due to study procedures. The consent process should start after the subject has started treatment with tPA or after the decision to begin mechanical thrombectomy has been made, whichever occurs sooner. Most pre-study procedures are performed in accordance with standard of care (SOC) for IV tPA administration and mechanical thrombectomy and therefore must be performed prior to informed consent. In accordance with good clinical practice, study specific procedures that do not coincide with SOC should only be performed after written informed consent is obtained (e.g., collection of blood samples for PK or antibody analysis).

Subjects who have signed consent (or whose representatives have provided surrogate consent), and meet all inclusion and exclusion criteria, can be randomized into the study. Subjects will be randomized using the NeuroNEXT Interactive Web Response System (IWRS) to either 3K3A-APC or placebo (in a 3:1 ratio). The Investigator, or designee, should randomize the subject in the IWRS to receive a unique subject number, which will also be linked to the allocated treatment assignment. Clinical staff will receive confirmation of the randomization, but remain blinded to the treatment assignment. Subjects who receive mechanical thrombectomy only should be randomized close to the start of the procedure (arterial puncture) to ensure that they continue to meet eligibility. There are 22 groups of four subjects planned, but fewer may be enrolled should the study meet either of the early stopping criteria (see section 7). If at any time enrollment is so rapid that there are two consecutive cohorts in the DLT review period, subjects will be assigned to placebo until the earlier of the two cohorts has been completely reviewed. The additional placebo subjects will be closely monitored and enrollment may be discontinued if the number enrolled exceed what was planned for the study.

The NeuroNEXT IWRS system will also serve to inform the unblinded study pharmacist at each site of the treatment assignment. Immediately after randomization, an email notification will be sent informing the unblinded site pharmacist(s) of the new subject, his/her weight, the treatment assignment, and the dose (if assigned to drug). The study pharmacist will then use this information to prepare the investigational treatment. An actual pre-dose weight for each subject is preferred, as all investigational doses will be based on this weight. If a subject's weight was estimated for the purposes of study drug dose calculation, then an actual weight must be obtained within 24 hours of Dose 1.

It is important to confirm eligibility again close to the first investigational dose as the NIHSS score may drop below 5 during the time between randomization and the first dose of study drug. For this reason, a repeat NIHSS should be assessed:

- Immediately prior to Dose 1 infusion if the subject received tPA treatment only, OR
- Immediately prior to draping the subject in preparation for mechanical thrombectomy if the subject is to receive mechanical thrombectomy alone or in combination with tPA.

Randomized subjects who experience significant neurologic improvement (defined as an NIHSS score < 5) prior to receipt of study drug will be termed 'Early Responders'. These subjects, and other randomized subjects who do not go on to receive study treatment for any reason, will not be included in the study, and will be replaced in the randomization sequence and CRM cohort. Any subject who receives any amount of study drug or placebo, however, will be considered "Dosed" and will be followed to the end of the study.

